## 3. STUDY DESIGN

A two-year randomized controlled, single-blinded design in three outpatient non-academic settings within two mental health care organizations.

## 4. STUDY POPULATION

## 4.1 Population (base)

*Patients.* Approximately 800 patients between 18 and 65 years, that apply for individual psychotherapy or psychological treatment at one of the three research locations (Schagen, Deventer, Twello), will be asked to participate in the study. *Therapists.* Therapists are psychotherapists, psychologists or psychiatric nurses that work

at the three research locations. Trainees will be excluded from the study. Approximately 50 therapists will be included in the study.

## 4.2 Inclusion criteria

Patients that apply for outpatient individual psychiatric treatment in one of the three research locations.

## 4.3 Exclusion criteria

Exclusion criteria are: having a psychotic disorder as main diagnosis, having a current severe manic episode, a high risk of decompensation, insufficient language skills in Dutch reading and speaking. Patients will be randomly allocated to one of the three research conditions.

## 4.4 Sample size calculation

Performing an a priori power analyses for multilevel analysis is complicated, because one has to have a good estimate of the variance components in advance and these are usually unknown, especially for three level models and three research conditions (de Jong, Moerbeek & Van der Leeden, 2009). An a priori power analysis was performed for two research conditions, based on the variance components of previously collected data, which resulted in approximately 4 patients per therapist, and 50 therapists participating for a power of 0.80, which is generally considered to be sufficient. However, this analysis was performed with an intended moderate effect (Cohen's d = 0.50), whereas feedback metaanalysis shows a small effect (Cohen's d=0.30). Also, in the current study we have three research conditions, which is considerably more complicated to model. The difference between the two feedback conditions is most likely smaller than d=0.30. Another thing that needs to be considered is that the effect only applies to the "not on track" group. As this group consists of approximately 25% of the total patient group and we cannot identify this group beforehand, the number of patients that need to be included in the study needs to be four times as large as the results from the a priori power analysis.

A traditional a priori power analysis was performed in G\*Power 3.0.10 for F tests with repeated measures, three research groups, three repeated measures, a power coefficient of 0.80, an  $\alpha$  of 0.05, and a correlation of 0.70 between the repeated measures. This resulted in a needed sample size of 90 not on track patients. The total sample size needed would then be 360 patients. This analysis does not take into account that patients are nested within therapists and therapists will explain part of the variance. We know from a previous study that the intraclass correlation was 0.18 at the therapist level. A rule of thumb to correct for the variance at the therapist level is to use the formula for the design effect:  $1 + (k-1)^{*icc}$ , with k being the number of patient per therapist, we would get a design effect of: 1 + 3 \* 0.18 = 1,54. This means that  $1.54^{*}360 = 554$  patients need to be included in the study. As we expect that some of the data will not be valid, the number of 600 patients was chosen as targeted *N*.

The patient flow in the three research locations is large enough to make that number in the inclusion period, that is set at 6 months. Intermediate power analysis will be performed after six months. Based on the observed variance and estimated power for the included number of patients, the inclusion period may be prolonged. This will influence study duration.

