#### 8.2 Multivariate analysis

The data will be analysed using a three-level random intercept, random slope multilevel model, with repeated measures at level 1, patients within therapists at level 2 and therapists at level three. Randomisation takes place at the patient level (level 2). The OQ-45 total score is the dependent variable. The treatment conditions will be recoded into two dummy variables. Initial severity on the OQ-45 at start of treatment will be included in the model as a covariate for both the intercept and slope prediction.

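### Section 4.4 reports a multilevel power result that its own times-four rule turns into 800 patients for two arms, and never reconciles it with the 600 chosen for three

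*Protocol*

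**What the plan says.** Section 4.4 contains two power calculations.

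The first is for a multilevel model: "An a priori power analysis was performed for two research conditions, based on the variance components of previously collected data". Its result is "approximately 4 patients per therapist, and 50 therapists participating for a power of 0.80", at d = 0.50, which the section calls moderate. The section then lists reasons why this is optimistic. The feedback meta-analysis points to d = 0.30. There are three conditions and not two. On the contrast between the two feedback arms it says: "The difference between the two feedback conditions is most likely smaller than d=0.30". Finally, the effect is confined to the roughly 25% of patients who are not on track and cannot be identified in advance, so the number of patients "needs to be four times as large as the results from the a priori power analysis".

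The second is a G*Power calculation for a repeated-measures F test with three groups, three measurements, alpha 0.05, power 0.80 and correlation 0.70. No effect size is given. It yields 90 not-on-track patients, hence 360 in total, then 554 after a design effect of 1.54, and "the number of 600 patients was chosen as targeted".

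Section 2 poses two primary questions, both comparisons between arms: feedback against none, and expected-response feedback against routine monitoring feedback. Section 8.2 fixes the analysis as a "three-level random intercept, random slope multilevel model" with initial severity as a covariate. Sections 4.4 and 8.3 plan a power check at six months, after which inclusion may be prolonged.

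**The concern.** The multilevel calculation is the one closest to the planned analysis and the only one said to rest on observed variance components. Every qualification attached to it (smaller effect, more arms, effect in a quarter of patients) pushes the required number up. Yet the number adopted for three arms is below what that calculation and the times-four rule give for two. The section does not say why.

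A reader will take 600 as carrying power 0.80 for the primary questions. If it does not, a null result on either question could be read as evidence against feedback when the trial had little chance of detecting the effect it expected. The six-month check could also inherit the wrong yardstick.

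**Working it through.** **Inputs.** From Section 4.4: 4 patients for each of 50 therapists, two conditions, d = 0.50, power 0.80; 25% not on track; G*Power result 90; therapist intraclass correlation (ICC) 0.18; target 600. From Section 6.2: three arms, random allocation, no ratio given. I assume equal allocation and two-sided alpha 0.05.

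**1. Reproducing the protocol's figures.**
- F-test route: 90 × 4 = 360; 1 + 3 × 0.18 = 1.54; 1.54 × 360 = 554.4. The arithmetic is correct.
- The 90 cannot be checked directly, because no effect size is given. In the between-groups test it is reproduced at f = 0.30: non-centrality 0.30² × 90 × 3 / (1 + 2 × 0.70) = 10.125 on 2 and 87 df, power 0.806. In the group-by-time interaction it is reproduced at f of about 0.117: non-centrality 0.117² × 90 × 3 / (1 − 0.70) = 12.3 on 4 and 174 df, power 0.80. The document does not say which test was meant. For three groups, a between-groups f of 0.30 corresponds to d of about 0.64 (one group differs: 0.30 × 3/√2) to 0.73 (equal spacing: 0.30 × √6).
- Multilevel route: 4 × 50 = 200, or 100 per arm. As a plausibility check, a two-sample t test at d = 0.50 needs 128, and 128 × 1.54 = 197. The variance components are not shown, so this is not a reproduction.

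**2. Carrying the multilevel result through the times-four rule.** 200 × 4 = 800 for two arms, or 400 per arm.

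**3. What 600 provides.** 600 / 3 = 200 per arm; 200 × 0.25 = 50 not on track per arm, half of 100.

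**4. Power for one pair of arms, 50 not-on-track patients each.**
- Scaled multilevel result: power 0.80 corresponds to a standardised difference of 1.96 + 0.84 = 2.80 at 100 per arm. At 50 per arm it is 2.80 × √0.5 = 1.98, so power is Φ(1.98 − 1.96) = 0.51. At d = 0.30 it is 1.98 × 0.30/0.50 = 1.19, so power is Φ(1.19 − 1.96) = 0.22.
- Plain two-sample t test: no clustering, one time point.
- Therapist component removed: Section 5.1 lets each therapist have patients in all three arms, so therapist variance may drop out of the contrast. Then d becomes 0.50/√0.82 = 0.552, or 0.30/√0.82 = 0.331.
- Baseline adjustment without clustering, with an assumed correlation of 0.70 between baseline and outcome: d becomes 0.50/√0.51 = 0.70, or 0.30/√0.51 = 0.42.

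| Approach | d = 0.50 | d = 0.30 |
|---|---|---|
| Multilevel result scaled | 0.51 | 0.22 |
| Plain t test | 0.70 | 0.32 |
| ICC 0.18 removed | 0.78 | 0.37 |
| Baseline correlation 0.70 (assumed) | 0.93 | 0.55 |

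**5. First primary question, if both feedback arms are pooled against control (100 against 50).** The equivalent equal group size is 2 × 100 × 50 / 150 = 66.7. Scaled power at d = 0.50 is Φ(2.80 × √(66.7/100) − 1.96) = 0.63; without clustering it is 0.82. At d = 0.30 the two figures are 0.28 and 0.41.

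**The case against.** The best defence is that the multilevel 200 may not transfer to this trial. Neither its variance components nor its level of randomisation nor its definition of d (slope or end state) is given. The match with 128 × 1.54 may mean that it carries a full design effect, as it would if therapists had been randomised. Here patients are randomised within therapists. If the ICC drops out of the contrast, about 53 not-on-track patients per arm give power 0.80 at d = 0.50, or 53 × 3 × 4 = 636 in total, close to 600. Repeated measures and adjustment for initial severity could raise power further. This stands. A reader might infer from the plain t test that power is at most 0.70 at d = 0.50; the documents do not support that ceiling.

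Two other strong readings also fail. A reader might say that the protocol's own analysis gives 1200 for three arms. Keeping 400 per arm does lead there (3 × 400), but that is an extrapolation and the protocol states no such number. A reader might also say that the protocol promises 0.80 for each pair of arms. It attaches 0.80 to a three-group F test.

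It can further be said that the section itself presents the multilevel analysis as limited, reuses its 4 patients per therapist in the design effect, and schedules a power check on observed variance. All true. But its stated limits argue for a larger number, reusing the 4 does not reconcile 800 with 600, and a later check does not correct the stated basis for 600. Sections 4.4 and 8.3 also leave open which model that check uses.

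**Conclusion.** The inconsistency is real and lies within Section 4.4: 800 patients for two arms by the section's own model-based result and multiplier, against 600 for three arms from a different test with an undisclosed effect size. This assumes that the times-four sentence refers to the multilevel analysis described just before it, which is how the paragraph reads.

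The documents do not settle whether 600 falls short at d = 0.50. Pairwise power runs from about 0.51 to above 0.90 depending on clustering and baseline adjustment, and the variance components that would decide it are not given. At d = 0.30 the conclusion is firmer. Pairwise power is about 0.22 to 0.37 under the first three approaches and about 0.55 with an assumed baseline correlation of 0.70, all well below 0.80. The section expects the contrast between the two feedback arms to be smaller still. These figures assume equal allocation, 25% not on track and no multiplicity adjustment.

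**What to change.** In Section 4.4:
- Carry the multilevel result through the times-four rule and explain how it relates to 600.
- State the effect size, and which effect was tested, behind the 90.
- Replace the implied 0.80 by the power that the Section 8.2 model gives at 600 patients for each of the two primary comparisons, at d = 0.50 and at d = 0.30, using the variance components already held and randomisation within therapists.

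In Section 8.3, name that model, with its variance components updated from the observed data, as the basis of the six-month power analysis.

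The cost is a rerun of an analysis that the investigators already have and a few sentences of text. The target can stay at 600; the stated power will probably be less favourable.

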## 2. OBJECTIVES

Primary Objectives:

- 1) Does providing therapists with feedback about their patients improve patient outcomes?
- 2) Does providing feedback based on an expected treatment response result in better outcomes than routine outcome monitoring feedback?

Secondary Objectives:

- 1) Can therapists accurately predict their patient's progress, with or without getting feedback?
- 2) Are therapists' feedback propensity and goal commitment predictive of better outcomes in the feedback conditions?

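### The 0.80 power that fixes the sample size belongs to an omnibus three-group F test and does not carry over to primary question 2 (ETR versus ROM feedback), which has about 0.25 to 0.38 at the protocol's own upper bound of d = 0.30

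*Protocol*

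**What the plan says.** Section 2 (Objectives) sets two primary questions. The first is whether feedback to therapists improves patient outcomes. The second reads "Does providing feedback based on an expected treatment response result in better outcomes than routine outcome monitoring feedback". Question 2 is a comparison of two arms.

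Section 4.4 first mentions a two-condition multilevel power analysis at d = 0.50 and sets it aside: "whereas feedback metaanalysis shows a small effect (Cohen's d=0.30"). It adds "The difference between the two feedback conditions is most likely smaller than d=0.30". It also says that the effect applies only to patients who are not on track, and that "this group consists of approximately 25% of the total patient group".

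The number that fixes the trial comes from a second calculation, "performed in G\*Power 3.0.10 for F tests with repeated measures, three research groups, three repeated measures, a power coefficient of 0.80", with alpha "of 0.05, and a correlation of 0.70 between the repeated measures". "This resulted in a needed sample size of 90 not on track patients". This is multiplied by four to give 360, then by a design effect of 1.54 to give 554, and raised to 600. The section states neither the effect size entered nor whether the F test was the between-group, within-group or interaction variant. It gives no power for either primary question in the three-arm design.

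Section 8.2 plans a three-level model with two dummy variables for condition.

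**The concern.** A three-group F test can be significant because feedback differs from control, while ETR and ROM do not differ at all. Its power is therefore not the power to detect an ETR-ROM difference. Section 4.4 gives 0.80 as the only power figure for the three-arm design and expects the ETR-ROM difference to be small, but does not connect the two.

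Question 2 is the trial's test of whether the prediction model adds anything to ordinary progress feedback. Someone who takes 0.80 as the chance of answering it would read a non-significant result as evidence that the model adds nothing. If the true power is far lower, a null result is the likely outcome even when a difference exists.

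**Working it through.** **Inputs from the protocol.** Section 4.4: three groups, three measures, power 0.80, alpha 0.05, correlation 0.70, 90 not-on-track patients, 25% not on track, design effect 1.54, target 600, ETR-ROM difference below d = 0.30. Section 6.2: random allocation to three conditions.

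**Assumptions, because the protocol is silent.** Equal allocation; d = 0.30 applies to not-on-track patients and is expressed in single-measurement SD units; the contrast is on the mean of three measures.

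**1. The plan's own figure.** For the between-group variant, the non-centrality is λ = N·m·f² / (1 + (m − 1)ρ). With N = 90, m = 3, ρ = 0.70 and an assumed f = 0.30:

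λ = 90 × 3 × 0.09 / 2.4 = 10.1, and F(2, 87) has power 0.806.

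N = 87 gives 0.79, so 90 is the smallest multiple of three that reaches 0.80. The figure is reproduced, but f = 0.30 is inferred and not stated. The rest of the chain also reproduces: 90 × 4 = 360 and 360 × 1.54 = 554.4.

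**2. Not-on-track patients per arm.**
- Before the nesting correction and the margin: 90 / 3 = 30.
- Target of 600, counted in full: 600 × 0.25 / 3 = 50.
- Target of 600 after the protocol's correction: 50 / 1.54 = 32.5.

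**3. Power for ETR versus ROM.** The mean of three measures has SD √((1 + 2 × 0.70)/3) = √0.80 = 0.894. The non-centrality of the two-sample t test is (d / 0.894) × √(n/2), with 2n − 2 degrees of freedom.

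| n per arm | d = 0.30: non-centrality | power | d = 0.20: non-centrality | power |
|---|---|---|---|---|
| 30 | 1.30 | 0.25 | 0.87 | 0.14 |
| 32.5 | 1.35 | 0.27 | 0.90 | 0.14 |
| 50 | 1.68 | 0.38 | 1.12 | 0.20 |

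Power of 0.80 at d = 0.30 would need about 140 not-on-track patients per arm, or about 140 × 3 × 4 = 1,680 patients before any design effect.

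**4. Sensitivity.** If d = 0.30 is taken on a change score, with SD √(2 × 0.30) = 0.775, power is 0.31 at 30 per arm and 0.48 at 50. It stays well below 0.80.

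**5. Question 1 under the omnibus assumptions.** Power of exactly 0.80 for F(2, 87) needs λ = 9.97. With equal arms, pooled feedback versus control and ETR versus ROM are orthogonal contrasts with variance factors 1.5/n and 2/n, so their squared non-centralities add up to λ. Let r be the ETR-ROM difference divided by the feedback-control difference. The share of λ in question 2 is (r²/2) / (r²/2 + 1/1.5).

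With ROM midway between control and ETR, r = 2/3 and the share is 0.222 / (0.222 + 0.667) = 0.25. Question 1 then has non-centrality √(0.75 × 9.97) = 2.73 and power 0.77 at 30 per arm. At 50 per arm it is 0.94. If ROM lies closer to ETR than midway, question 1 gains power and question 2 loses it.

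**The case against.** The strongest reply is that section 4.4 claims no more than it computed. It names the test, says there are three groups, warns that the ETR-ROM difference is probably smaller, and never attributes 0.80 to each question. Sections 4.4 and 8.3 plan a power analysis at six months, after which inclusion may be prolonged. The planned model uses up to 15 session scores with baseline severity as a covariate, so a t contrast on three measures is not its power. Patients of one therapist can be in all three conditions, so dividing by 1.54 may be too severe.

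Much of this stands. The figures above approximate the power on the protocol's own sizing basis, not the power of the final model, and 50 per arm is shown because the correction may be conservative. The six-month analysis does not close the gap, because the protocol does not say which comparison it will address.

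Three stronger readings are tempting and not supported:
- **That the two questions cannot both reach 0.80.** At 30 per arm the equal split gives 0.60 each. At 50 per arm, λ rises to 9.97 × 50/30 = 16.6 and the equal split gives 0.82 each. That split needs an ETR-ROM difference 1.15 times the feedback-control difference, about d = 0.52, so it does not rescue question 2, but the impossibility is not general.
- **That question 2 has up to about 0.53 at 30 per arm, or 0.35 with equally spaced arms.** These values follow from dividing up the omnibus signal, but imply ETR-ROM differences of about d = 0.48 and d = 0.36, above the protocol's 0.30. Nor does the protocol give any ratio between the two differences from which to derive a lower limit.
- **That question 1 is also badly underpowered.** Under the omnibus assumptions it is not.

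**Conclusion.** The point holds for question 2. The 0.80 behind the sample size is the power of an omnibus test that by itself answers neither primary question, and the protocol's own figures put the ETR-ROM comparison far below it: about 0.25 (30 per arm) to 0.38 (50 per arm) at d = 0.30, and lower for the smaller differences that section 4.4 considers more likely. This rests on equal arms, on d = 0.30 referring to not-on-track patients, and on the mean of three measures at correlation 0.70. The change-score alternative raises the figures without altering the conclusion.

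Question 1 has about 0.77 or more when ROM lies at or above midway between control and ETR. That depends on the omnibus effect size being right. The inferred f = 0.30 corresponds to an ETR-control difference of about d = 0.64 to 0.73, which is one reason why the effect size entered needs to be stated.

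**What to change.** In section 4.4:
- Label 0.80 as the power of the omnibus three-group F test only.
- State the effect size and the F-test variant entered in the calculation.
- State the power for ETR versus ROM at the planned sample size: at most about 0.25 to 0.38 among not-on-track patients at d = 0.30, with the assumptions listed (mean of three measures, correlation 0.70, equal arms, two-sided alpha 0.05, 30 to 50 per arm).
- State that a non-significant result on question 2 will be reported with its confidence interval and not interpreted as showing that the prediction model adds nothing.

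This is a change of wording. It needs no extra patients and leaves the model and the primary questions as they are. The only downside is a less favourable stated power.

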#### 1. INTRODUCTION AND RATIONALE

A large body of research, performed over 40 years, has demonstrated the general effectiveness of psychological treatments (Lambert & Ogles, 2004). However, while treatment is beneficial for many patients, not all patients profit from therapy. In randomized controlled clinical trials, where treatment is provided under more or less optimal conditions, an average of 67% of patients is statistically reliably improved at the end of treatment. In clinical practice, the success rates are much lower: in an American national database of more than 6000 patients, only 35% of the patients was improved (Hansen, Lambert, & Forman, 2002).

Riemer & Bickman (2003) consider feedback interventions a promising approach to improve clinical practice. According to them, clinicians need to have more systematic and reliable information about the status of their patients, so that they are capable of adjusting their treatment. Literature from psychology, educational science and medicine shows the effectiveness of feedback interventions (e.g. Kluger & DeNisi, 1996, 1998; Jamtvedt et al., 2006; Hattie & Timperley, 2007; Veloski et al., 2006). A general meta-analysis by Kluger & DeNisi (1996) showed an average effect size of 0.38 for feedback interventions. More specifically tailored to the effectiveness of health status feedback to professionals, a meta-analysis by Sapyta (2004, in Sapyta, Riemer, & Bickman, 2005) found an average effect size of 0.21. Further analysis showed that feedback on 'flagged patients' (those not progressing well in treatment) had an average effect size of 0.31, while there was no significant feedback effect for the 'non-flagged' samples.

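### Section 4.4 derives 90 not-on-track patients for power 0.80 without stating the effect size; at the d = 0.30 it takes from the evidence, power is well below 0.80

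*Protocol*

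**What the plan says.** Section 4.4 first describes a two-arm multilevel power analysis at d = 0.50 and qualifies it: "whereas feedback metaanalysis shows a small effect (Cohen's d=0.30". On the comparison of the two feedback arms it adds: "The difference between the two feedback conditions is most likely smaller than d=0.30". It also says that the effect applies only to not-on-track patients, about 25% of the total. The Introduction (section 1) gives a meta-analytic figure for flagged patients, who "had an average effect size of 0.31".

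The calculation behind the target comes next: "A traditional a priori power analysis was performed in G\*Power 3.0.10 for F tests with repeated measures", with "three research groups, three repeated measures, a power coefficient of 0.80", an alpha "of 0.05, and a correlation of 0.70 between the repeated measures". The result is: "This resulted in a needed sample size of 90 not on track patients". This is multiplied by four to give 360, then by a design effect of 1.54 to give 554, and rounded up to 600.

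Section 2 has two primary objectives: whether feedback improves outcome, and whether expected-treatment-response (ETR) feedback does better than routine monitoring (ROM) feedback.

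**The concern.** A repeated-measures F test cannot return a sample size without an effect size, and none is given. The section has just set d = 0.30 against its earlier 0.50, so a reader will naturally take the 90 as sized for about 0.30. If it was in fact sized for roughly twice that, the trial is much less sensitive than it appears, and a null result could be misread as evidence against feedback.

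Two things add to this. The test is a three-group omnibus test, so it says nothing about power for ETR versus ROM. And the power analysis planned at six months (sections 4.4 and 8.3), which may prolong inclusion, has no stated effect size to work from.

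**Working it through.** **Inputs from section 4.4.** Groups k = 3, measures m = 3, correlation r = 0.70, alpha 0.05, power 0.80, 25% not on track, therapist intraclass correlation 0.18, target 600. Effect size, sub-test and nonsphericity epsilon (ε) are not stated.

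**1. The stated chain.** 4 × 90 = 360. 1 + 3 × 0.18 = 1.54. 1.54 × 360 = 554.4. These sums are correct. The question is the 90.

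**2. Reproducing the 90** (noncentral F, N in multiples of 3).

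Between factors: λ = f² × N × m / (1 + (m − 1) × r), with df k − 1 and N − k. For f = 0.30 and N = 90, λ = 0.09 × 90 × 3 / 2.4 = 10.125 on 2 and 87 df, and power is 0.806. At N = 87 it is 0.791. So f = 0.30 gives exactly 90.

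Group-by-time interaction: λ = f² × N × m × ε / (1 − r), with df (k − 1)(m − 1)ε and (N − k)(m − 1)ε. This also gives 90 at several settings:

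| f | ε | Power at N = 90 |
|---|---|---|
| 0.117 | 1 | 0.802 |
| 0.1225 | 0.9 | 0.810 |
| 0.141 | 0.6 | 0.811 |
| 0.15 | 0.5 | 0.806 |

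**3. Cohen's f and d are different scales** (between factors).

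| Pattern of means | f from d | f at d = 0.30 | d at f = 0.30 | Not-on-track patients for 0.80 at d = 0.30 |
|---|---|---|---|---|
| Two-group conversion | d/2 | 0.15 | 0.60 | 348 |
| Both feedback arms better by d | d√2/3 | 0.141 | 0.64 | 390 |
| Three equally spaced arms | d/√6 | 0.122 | 0.73 | 519 |

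**4. What d = 0.30 means in the interaction test.** There f measures only the group-by-time component. Assume no difference at the first of three measures and d = 0.30 at the last. With linear divergence, f is 0.050 (equally spaced arms) to 0.058 (both feedback arms better). If the difference appears only at the last measure, f is 0.058 to 0.067. All are well below the 0.117 to 0.15 that returns 90.

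**5. Power at d = 0.30.** The 600 patients include about 0.25 × 600 = 150 not on track; dividing by the protocol's 1.54 gives about 97 effective. Contrasts use two-sided t tests with equal arms. The mean of three measures has variance (1 + 2 × 0.70)/3 = 0.80. A final measure adjusted for baseline has residual variance 1 − 0.70² = 0.51.

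| Test | 90 | 97 | 150 |
|---|---|---|---|
| Between-factors omnibus | 0.19–0.27 | 0.20–0.29 | 0.30–0.43 |
| Interaction, f 0.05–0.067, ε = 1 | 0.19–0.31 | 0.20–0.34 | 0.30–0.51 |
| Interaction, f 0.05–0.067, ε = 0.5 | 0.14–0.22 | 0.15–0.23 | 0.21–0.35 |
| Pooled feedback v control, mean of three | 0.32 | 0.34 | 0.49 |
| Pooled feedback v control, baseline-adjusted | 0.46 | 0.49 | 0.67 |
| ETR v ROM, mean of three | 0.25 | 0.26 | 0.38 |
| ETR v ROM, baseline-adjusted | 0.36 | 0.38 | 0.55 |

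The protocol expects ETR versus ROM to be below 0.30. At an assumed d = 0.20 with 50 against 50, power is about 0.20 (mean of three) to 0.28 (baseline-adjusted), before any design effect.

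**6. Effect detectable with power 0.80.** With 150 and no design effect, the omnibus test needs f = 0.229, which is d = 0.46 to 0.56 by the conversions in step 3. The baseline-adjusted contrasts need d of about 0.35 (pooled) and 0.40 (ETR v ROM).

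**The case against.** The strongest reply is that the sub-test and epsilon are not given, so no error in the run can be shown. The three f values that correspond to d = 0.30 each return 90 in the interaction test at some epsilon, and a trial about progress over time could well have used that test. This stands. A reader might infer that 90 can come only from f = 0.30, or that d was certainly entered as f; the documents support neither. But the interaction route does not restore 0.80: an f of 0.12 to 0.15 on the group-by-time component is far more than a final difference of 0.30 produces (step 4). That conclusion does rest on how the difference is assumed to develop, which the protocol does not state.

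A reader might also infer that the protocol promises 0.80 power for d = 0.30. It never says so. It cites d = 0.30 as a caution about the earlier two-arm calculation and then quotes 0.80 with no effect attached. Section 1 also reports effects of 0.34 to 0.92 in at-risk patients from earlier controlled studies, and 0.60 to 0.73 lies inside that range. A larger effect may have been intended, but section 4.4 does not invoke it.

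Finally, the planned analysis (section 8.2) is a three-level model of session-by-session scores adjusted for initial severity, not a three-measure F test. Its power could be higher, which is why the adjusted contrasts are shown and why one narrow range such as 0.2 to 0.5 would be too confident. The six-month check may prolong inclusion, but it is described in terms of observed variance and names no effect size.

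**Conclusion.** The point holds in this form: the 0.80 behind 90, 360, 554 and 600 has no stated effect size, and it does not hold for the d = 0.30 that section 4.4 takes from the evidence. The most likely source of the 90 is f = 0.30 between factors, about d = 0.60 to 0.73, roughly twice 0.30; this is likely, not proven.

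At d = 0.30 no setting worked through above reaches 0.80. The size of the shortfall depends on three assumptions: r = 0.70, whether the design effect of 1.54 applies, and whether d refers to an average or a baseline-adjusted final difference. Power for the second primary question is not addressed by the calculation at all, and at the effect below 0.30 that the protocol expects it is lower still.

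**What to change.** In section 4.4:

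- State the f that was entered, its d equivalent, the sub-test and epsilon. If an effect larger than 0.30 was intended, say so and give the source.
- Replace the unqualified 0.80 with the power that 600 patients (about 150 not on track) give at d = 0.30, or with the effect detectable at 0.80. Show the assumed correlation, design effect and pattern of means.
- Report this separately for feedback versus control and for ETR versus ROM.

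In sections 4.4 and 8.3, state that the six-month power analysis uses that corrected effect size, held fixed, so that only the variance estimates are updated.

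The cost is a short recalculation and protocol wording. The stated power becomes less favourable. No extra patients are required.
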